8.2.5. Suicidal Ideation and Behaviour Risk Monitoring

GSK3640254 is not a central nervous system active drug nor is it being developed for a neurologic or psychiatric condition. However, given the risk of suicidal ideation identified with a previous MI compound, GSK3532795, all participants will undergo screening using the C-SSRS administered by a clinician (or qualified designee); any positive (abnormal) response confirmed by the investigator, will exclude them from participating. Repeat assessments will be performed during the treatment phase of the study. In case of a positive (abnormal) response confirmed by the investigator, the participant will undergo immediate clinical assessment of suicidality (by the investigator or a consulting psychiatrist). Emergence of new onset suicidal ideation or a Grade 3 or higher psychiatric AE will result in immediate discontinuation and urgent specialist psychiatric evaluation and management.

The definitions of behavioral suicidal events used in this scale are based on those used in the Columbia-Suicide History Form [Posner, 2007]. Questions are asked on suicidal behavior, suicidal ideation, and intensity of ideation. Screening visit questions will be in relation to lifetime experiences and current experiences (within the past 2 months) and all subsequent questioning in relation to the last assessment.

Emergent non-suicidal psychiatric AE evaluation and management:

- Any DAIDS Grade 1 or 2 psychiatric AE: A Grade 1 or 2 psychiatric AE may result in additional unscheduled visits (in-clinic or at home) as clinically indicated. This may include a more in-depth assessment of the AE through interview, additional unscheduled clinical laboratory tests, and/or imaging. Psychiatric consultation may be required at the discretion of the investigator. Any pharmacotherapy should be discussed with the Medical Monitor.
- Any DAIDS Grade 3 or 4 psychiatric AE: As described in Section 7.1.4, a Grade 3 or 4 psychiatric AE will result in discontinuation from the study and emergency psychiatric evaluation (including potential hospitalization and pharmacotherapy as indicated).

8.2.6. Gastrointestinal Intolerance Evaluation and Monitoring Plan (with Stopping Criteria)

Preclinical toxicology studies in rats and dogs have suggested a potential for GI related toxicity with GSK3640254.

Prior clinical trials have not evaluated for the presence of gastric toxicity in humans. Thus, it is unclear if any of the GI AEs observed in any clinical trial were representative of, associated with, or resulted from gastric toxicity (if present). This section provides general guidance to the investigator on the evaluation and management of primarily upper GI symptoms (Table 1). The investigator may contact the VH/GSK Medical Monitor to discuss evaluation and management (including discontinuation of a participant) of any GI symptoms throughout the study.

For any DAIDS Grade 4 or related Grade 3 AE, the investigator will discontinue the participant from the study and may perform an evaluation/management plan incorporating the elements in [Table 1](#).

Table 1 Gastrointestinal Toxicity Evaluation and Management

HISTORY	For symptoms of all grades, a thorough history forms the foundation of proper evaluation and management. The following are potential manifestations of some gastrointestinal (GI) clinical syndromes that may occur (possibly in combination) during the clinical study.
Abdominal Pain	The investigator should obtain information on chronology, location, intensity/character, aggravating and alleviating factors, and associated symptoms in the context of the participants' relevant past medical history [Millham , 2016]. With chronic symptoms, factors suggestive of an organic process include the following: fever, night sweats, loss of appetite, weight loss, and nocturnal awakening [Yarze , 2016]. The historical and physical examination should be efficient and lead to an accurate diagnosis soon after presentation.
Nausea and Vomiting	The investigator should attempt to identify the etiology of these symptoms (and whether they are intraperitoneal, extraperitoneal, medication related, infection related, or due to a metabolic disorder [Hasler , 2012]. Medications can cause nausea and vomiting acutely.
Dyspepsia	The investigator should identify the presence of red flags (odynophagia, unexplained weight loss, recurrent vomiting, GI bleeding, jaundice, palpable mass or adenopathy, or family history of GI malignancy). Symptoms of dyspepsia could include early satiety, bloating, or belching. Additionally, atypical symptoms of dyspepsia could include the following: pharyngitis, asthma, bronchitis, hoarseness, chest pain, or abdominal pain.
Diarrhea	Similar to other GI symptoms, important historical assessment includes duration, onset, pattern, epidemiology (e.g. travel and diet), aggravating or iatrogenic factors, alleviating factors, stool appearance, presence of other symptoms (e.g., abdominal pain), or weight loss. The differential can be narrowed if there are clear watery, inflammatory, or fatty manifestations [Schiller , 2016].
Other Clinical Syndromes	Additional diagnostic criteria for other GI disorders potentially encountered in the clinical study are available elsewhere [Rome Foundation , 2019].
PHYSICAL EXAMINATION	Physical examination should complement elements obtained from the history [Hasler, 2012]. The examination elements may include the following: auscultation for bowel sounds (up to 2 minutes if necessary) and palpation (including assessment for rebound, guarding, and muscular rigidity [Millham , 2016]). Acutely, the investigator may assess for signs of intravascular volume depletion (e.g., orthostasis) and/or aspiration of vomitus as appropriate. Abdominal tenderness and guarding may indicate inflammation. The presence of fecal blood can indicate mucosal damage (e.g., from an ulcer). Complete evaluation of dyspepsia should include an oral examination (poor dentition or pharyngeal erythema) and lungs for wheezing.
DIAGNOSTIC EVALUATION AND MANAGEMENT	A major goal in the diagnostic evaluation of a participant with upper GI symptoms is to quickly arrive at a final diagnosis without exposing the participant to unnecessary (invasive) testing; investigators should exercise good clinical judgment in this regard [Soll , 2009]. A major goal of therapy is directed at correcting the underlying identifiable medical or

	surgical abnormalities [e.g., perforation or infarction) [Malagelada, 2016]. Consultation (e.g., gastroenterologist) is recommended as clinically indicated. Emergent action should be taken as necessary: correction of hypovolemia or electrolyte abnormalities.
--	--

CCI - This section contained Clinical Outcome Assessment data collection questionnaires or indices, which are protected by third party copyright laws and therefore have been excluded.

8.2.7. COVID-19 Measures

The measures approved for implementation within this clinical trial to protect participant safety, welfare, and rights, and ensure data integrity and the integrity of the clinical trial, as a result of COVID-19 only, are outlined in [Appendix 7](#).

8.3. Adverse Events and Serious Adverse Events

The definitions of an AE or SAE can be found in [Appendix 6](#). As described in [Appendix 6](#), intensity of AEs (and laboratory abnormalities) will be graded using the most recent version of the DAIDS grading table at the time of the last participant last visit PPD

While the study population will consist of HIV-1 seronegative healthy participants, the DAIDS criteria is being used in later phase clinical studies (e.g., Phase 2); additionally, the DAIDS criteria have a more conservative grading scale relative to other scales (e.g.,

Common Terminology Criteria for Adverse Events v 4.0). Thus, participant safety evaluation and monitoring will be more conservative.

The investigator and any qualified designees are responsible for detecting, documenting, and reporting events that meet the definition of an AE or SAE and remain responsible for following up on AEs that are serious, considered related to the study intervention or the study, or that caused the participant to discontinue the study (see Section 7).

See Section 10.7.3.2 for the assessment and recording of AEs and SAEs related to COVID-19.

8.3.1. Time Period and Frequency for Collecting AE and SAE Information

- All SAEs will be collected from the signing of the ICF until the end of the study at the time points specified in the SoA (Section 1.3).
- All AEs will be collected from the start of intervention until the end of the study at the time points specified in the SoA (Section 1.3).
- Medical occurrences that begin before the start of study intervention but after obtaining informed consent will be considered medical history, not an AE, and will be recorded in the source documents.
- All SAEs will be recorded and reported to the sponsor or designee immediately, and under no circumstance should this exceed 24 hours, as indicated in Appendix 6. The investigator will submit any updated SAE data to the sponsor within 24 hours of it being available.
- Investigators are not obligated to actively seek AEs or SAEs after the conclusion of the study participation. However, if the investigator learns of any SAE, including a death, at any time after a participant has been discharged from the study, and he or she considers the event to be reasonably related to the study intervention or study participation, the investigator must promptly notify the sponsor.

8.3.2. Method of Detecting AEs and SAEs

- The method of recording, evaluating, and assessing causality of AEs and SAEs and the procedures for completing and transmitting SAE reports are provided in Appendix 6.
- Care will be taken not to introduce bias when detecting an AE and/or SAE. Open-ended and non-leading verbal questioning of the participant is the preferred method to inquire about AE occurrence. Participants will be questioned prior to each dose of study intervention.

8.3.3. Follow-up of AEs and SAEs

After the initial AE/SAE report, the investigator is required to proactively follow each participant at subsequent visits/contacts. All SAEs and non-serious AEs of special interest (as defined in Section 8.3.6) will be followed until the event is resolved,

stabilized, otherwise explained, or the participant is lost to follow-up (as defined in Section 7.3). Further information on follow-up procedures is given in [Appendix 6](#).

8.3.4. Regulatory Reporting Requirements for SAEs

- Prompt notification by the investigator to the sponsor of an SAE is essential so that legal obligations and ethical responsibilities towards the safety of participants and the safety of a study intervention under clinical investigation are met.
- The sponsor has a legal responsibility to notify both the local regulatory authority and other regulatory agencies about the safety of a study intervention under clinical investigation. The sponsor will comply with country-specific regulatory requirements relating to safety reporting to the regulatory authority, IRBs/IECs, and investigators.
- For all studies except those utilizing medical devices, investigator safety reports must be prepared for suspected unexpected serious adverse reactions (SUSAR) according to local regulatory requirements and sponsor policy and forwarded to investigators as necessary.
- An investigator who receives an investigator safety report describing a SAE or other specific safety information (e.g., summary or listing of SAEs) from the sponsor will review and then file it along with the CIB and will notify the IRB/IEC, if appropriate according to local requirements.

8.3.5. Pregnancy

- Details of all pregnancies in female participants and, if indicated, female partners of male participants will be collected after the start of study intervention through the end of pregnancy (termination or delivery).
- If a pregnancy is reported, the investigator should inform GSK within 24 hours of learning of the pregnancy and should follow the procedures outlined in [Appendix 3](#).
- Abnormal pregnancy outcomes (e.g., spontaneous abortion, fetal death, stillbirth, congenital anomalies, ectopic pregnancy) are considered SAEs.
- A spontaneous abortion (occurring at <22 weeks gestational age) or stillbirth (occurring at >22 weeks gestational age) is always considered to be an SAE and will be reported as such.

8.3.6. Adverse Events of Special Interest

Adverse events of special interest include all AEs classified in the cardiovascular (per the Medical Dictionary for Regulatory Activities) system organ class, seizure, and syncope. Additional AEs of special interest within other system organ classes (e.g., GI, neurologic, rash, or psychiatric) may be defined in the reporting and analysis plan.

8.4. Treatment of Overdose

For this study, any dose of GSK3640254 greater than the planned dose within a 24-hour time period (± 2 hours) will be considered an overdose.

VH/GSK does not recommend specific treatment for an overdose. The investigator will use clinical judgment to treat an overdose.

In the event of an overdose, the investigator should:

1. Contact the Medical Monitor immediately.
2. Closely monitor the participant for AE/SAE and laboratory abnormalities until GSK3640254 can no longer be detected systemically (at least 5 days).
3. Obtain a plasma sample for PK analysis immediately and through 7 days after the date of the last dose of study intervention if requested by the Medical Monitor (determined on a case-by-case basis).
37. Document the quantity of the excess dose as well as the duration of the overdosing in the CRF.

Decisions regarding dose interruptions or modifications will be made by the investigator in consultation with the Medical Monitor based on the clinical evaluation of the participant.

8.5. Pharmacokinetics

- Whole blood samples of approximately 2 mL will be collected for measurement of plasma concentrations of GSK3640254 and moxifloxacin as specified in the SoA (Section 1.3).
- A maximum of 10 samples (approximately 20 mL) may be collected at additional time points during the study if warranted and agreed upon between the investigator and the sponsor. Instructions for the collection and handling of biological samples will be provided by the sponsor. The actual date and time (24-hour clock time) of each sample will be recorded.
- Samples will be used to evaluate the PK of GSK3640254 and moxifloxacin. Samples collected for analyses of plasma concentrations may also be used to evaluate safety aspects related to concerns arising during or after the study.
- Once the plasma has been analysed for GSK3640254 and moxifloxacin, any remaining plasma will be analysed for other compound-related metabolites and the results provided in a separate report.

8.6. Cardiodynamic Assessments

Not Applicable

8.6.1. Continuous Holter Electrocardiograms

Pre-dose digital 12-lead ECGs will be extracted in replicates from continuous Holter recordings. On Day -1 (Baseline), continuous Holter ECG recordings will be extracted at the following time points (relative to the time of planned dosing on the next day): pre-dose at -45, -30, and -15 minutes, and then after the time of planned dosing at 0.5, 1, 2, 3, 3.5, 4, 4.5, 5, 6, 8, 10, 12, and 24 hours. The Holter ECG should be started approximately 2 hours before dosing on Day 1 of each period, and ECG extractions will occur at -45, -30, and -15 minutes before dosing. On Day 7, 12-lead ECGs will be extracted from continuous Holter recordings pre-dose (single time point) and after the morning dose at 0.5, 1, 2, 3, 3.5, 4, 4.5, 5, 6, 8, 10, 12, and 24 hours in each period.

Electrocardiograms will be extracted from the continuous recording by a central ECG laboratory (ERT, Rochester, NY). The ECGs will be extracted from the continuous recording during an extraction window of 5 minutes prior to the nominal time point. Each ECG extraction window will be preceded by an approximate 15-minute supine rest period in an undisturbed environment.

The ECG extractions will be time-matched to the PK samples, but will be obtained before the actual PK sampling time to avoid changes in autonomic tone associated with the psychological aspects of blood collection as well as the reduction in blood volume subsequent to blood collection. When time points for assessments coincide, the order should be safety ECGs, vital signs, ECG extraction, and then PK blood collection.

The following ECG parameters will be measured and calculated: HR, PR interval, QTcF, QRS interval, T-wave morphology, and U-wave presence.

8.6.2. Cardiodynamic Sample Analysis

The primary analysis will be based on C-QTc modeling of the relationship between GSK3640254 plasma concentration and change-from-baseline QTcF (Δ QTcF) with the intent to exclude an effect of $\Delta\Delta$ QTcF > 10 ms at clinically relevant plasma levels of GSK3640254.

In addition, the effect of GSK3640254 on placebo-corrected change-from-baseline in QTcF, HR, PR, and QRS ($\Delta\Delta$ QTcF, $\Delta\Delta$ HR, $\Delta\Delta$ PR, and $\Delta\Delta$ QRS) will be evaluated at each post-dose time point (“by-time point” analysis) using the intersection union test. An analysis of categorical outliers will be performed for changes in HR, PR, QRS, QTcF, T-wave morphology, and U-wave presence.

Assay sensitivity will be evaluated by C-QTc analysis of the effect on ($\Delta\Delta$ QTcF) of moxifloxacin using the same model as for the primary analysis. Assay sensitivity will be deemed met if the slope of the C-QTc relationship is statistically significant at the 10% level in a 2-sided test and the predicted QTc effect (i.e., the lower bound of the 2-sided 90% CI of $\Delta\Delta$ QTcF) is above 5 ms at the observed geometric mean Cmax of 400 mg moxifloxacin.

For all continuous ECG parameters from each period, baseline will be the average of the derived ECG intervals from the 3 ECG time points prior to dosing (-45, -30,

and -15 minutes) on Day 1 for the respective period. For T-wave morphology and U-wave presence, baseline includes any findings observed in any replicates from the 3 pre-dose time points (-45, -30, and -15 minutes) on Day 1 in each period.

8.7. Genetics

Genetics are not evaluated in this study.

8.8. Biomarkers

Biomarkers are not evaluated in this study.

8.9. Immunogenicity Assessments

Immunogenicity is not evaluated in this study.

8.10. Medical Resource Utilization and Health Economics

Medical resource utilization and health economics parameters are not evaluated in this study.

9. STATISTICAL CONSIDERATIONS

9.1. Statistical Hypotheses

There is no formal statistical hypothesis to be tested in Part 1.

For Part 2, the statistical hypothesis to be tested for the primary assessment of QT prolongation at the highest clinically relevant exposure using the C-QTc analysis for each active dose group is:

$$H_0: \Delta\Delta QTcF \geq 10 \text{ ms}$$

$$H_1: \Delta\Delta QTcF < 10 \text{ ms}$$

where $\Delta\Delta QTcF$ is the mean $\Delta\Delta QTcF$ at the mean Cmax for each active dose group, respectively.

In addition, the statistical hypothesis to be tested for the assay sensitivity using the C-QTc analysis is:

$$H_0: \Delta\Delta QTcF \leq 5 \text{ ms}$$

$$H_1: \Delta\Delta QTcF > 5 \text{ ms}$$

where $\Delta\Delta QTcF$ is the mean $\Delta\Delta QTcF$ at the mean Cmax for the moxifloxacin group.

9.2. Sample Size Determination

Part 1: A total of up to 16 participants are planned to be randomized, 8 participants per cohort (6 participants to receive GSK3640254 and 2 participants to receive placebo). For

Part 1, as there is no formal research hypothesis being statistically tested, the sample size is not selected based on statistical considerations but was determined using feasibility.

Part 2: A sample size of approximately 42 participants is chosen to obtain 34 evaluable participants to complete the study. A sample size of 34 evaluable participants will provide more than 90% power to exclude that active drug causes more than a 10-ms QTc effect at clinically relevant plasma levels, as shown by the upper bound of the 2-sided 90% CI of the model predicted QTc effect ($\Delta\Delta QTcF$) at the observed geometric mean Cmax of active drug in the study.

This power is estimated approximately using a paired t-test. The calculation assumes a one-sided 5% significance level, an underlying effect of GSK3640254 of 4 ms and a standard deviation (SD) of the ΔQTc of 8.5 ms for both active drug and placebo. [Table 2](#) provides the sample sizes for power of 90% and 95% with underlying effect of 3, 4, and 5 ms and SD of 8, 8.5, and 9.5 ms.

The C-QTc analysis method is supported by [Darpo, 2015](#) and [Ferber, 2015](#) and consistent with the experiences from 25 recent TQT studies in ERT, which provided SD=8 ms as a conservative estimate for general TQT studies. Note that this calculation is conservative also because it does not take into account any gain in precision due to the use of all data of each participant with the help of a linear mixed effects model. An SD of 9.5 ms is a conservative value used in previous MI compound BMS-663068 and AI compound Fostemsavir TQT studies in GSK. In the previous GSK3640254 FTIH Study 207187 SAD/MAD study, the within-participant SD based on by-time point analysis was 8.5 ms, which provides the conservative estimated SD for this compound. Therefore, the underlying effect 4 ms and SD=8.5 ms with 90% of power for the study sample size of 34 participants was chosen for this study. With the dropout rate of 20%, approximately 42 participants will be enrolled to ensure the evaluable number of participants is greater or equal to 34.

Table 2 Sample Size Determination - Power

Sample size	Number of Participants for 90% Power	Number of Participants for 95% Power
Underlying effect 3 ms SD = 8 ms	22	28
Underlying effect 3 ms SD = 8.5 ms	25	32
Underlying effect 3 ms SD = 9.5 ms	32	40
Underlying effect 4 ms SD = 8 ms	30	38
Underlying effect 4 ms SD = 8.5 ms	34	43
Underlying effect 4 ms, SD = 9.5 ms	43	54
Underlying effect 5 ms SD = 8 ms	44	55
Underlying effect 5 ms SD = 8.5 ms	49	63
Underlying effect 5 ms SD = 9.5 ms	62	78

Sample Size for Assay Sensitivity: To demonstrate assay sensitivity with C-QTc analysis, it must be shown that the $\Delta\Delta\text{QTcF}$ of a single dose of 400 mg moxifloxacin exceeds 5 ms (i.e., the lower bound of the 2-sided 90% CI of the predicted QTc effect [$\Delta\Delta\text{QTcF}$] should exceed 5 ms).

In a similarly designed, recent crossover study with 24 healthy participants (on-file data, ERT), the standard error (SE) for the prediction of the QT effect of moxifloxacin based on the C-QTc analysis was 1.24 ms. The within-subject SD of ΔQTcF in this study was 5.4 ms based on the by-time point analysis. If the effect of moxifloxacin is assumed to be 10 ms, the SE of 1.24 ms corresponds to an effect size of $(10-5)/(1.24 \times \sqrt{24}) = 0.82$, where the effect size is the effect assumed under the alternative hypothesis divided by the SD of the test variable. This value should be compared to the effect size of 0.62 required to guarantee a power of at least 95% in a paired *t*-test situation with a sample size of 30 evaluable participants. In other words, based on this calculation, a power of at least 95% for 30 evaluable participants will be obtained as long as the variability of the ΔQTcF , as measured by its within-subject SD, does not exceed 7.1 ms (i.e., 132% of the 5.4 ms observed in the above referenced study [on-file data, ERT]) assuming the ratio of effective sizes is consistent with inverse ratio of within-subject SD. The number also agrees with recent recommendations of the FDA, which propose at least 20 participants [Huang, 2019].

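### Section 9.2 slightly overstates both the power at 34 evaluable participants (88.6% by the named paired t-test, not more than 90%) and the yield from 42 enrolled at 20% dropout (33.6 expected, not an assured 34)

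*Protocol*

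**What the plan says.** Protocol Section 9.2 opens the Part 2 justification with this claim: "A sample size of 34 evaluable participants will provide more than 90% power". The power in question is for ruling out a QTc effect above 10 ms. The method is named: "This power is estimated approximately using a paired t-test". For the inputs, the section takes a one-sided 5% level and "an underlying effect of GSK3640254 of 4 ms". Variability is entered as a single value for each treatment, the "standard deviation (SD) of the ΔQTc of 8.5 ms for both active drug and placebo". Later the section describes the same choice as having 90% power, without the words more than.

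Table 2 lists, for "Underlying effect 4 ms SD = 8.5 ms", 34 participants for 90% power and 43 for 95%. The section also calls the calculation conservative, because it ignores the precision that a linear mixed-effects model gains from using all of each participant's data.

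On enrolment, Section 9.2 says: "With the dropout rate of 20%, approximately 42 participants will be enrolled to ensure the evaluable number of participants is greater or equal to 34". The Synopsis (Section 1.1) and Section 4.1 likewise say that about 42 will be randomized to ensure 34 evaluable participants with data from all periods.

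**The concern.** The power statement and the enrolment figure are the stated basis for the primary objective, excluding a 10-ms effect. A reader who applies the named test to the stated inputs does not get above 90% at 34, and does not reproduce Table 2. The dropout step is also rounded in the favourable direction. Neither gap is large, but both run the same way, and the text is worded as a floor in each case (more than; ensure) where the calculation does not reach it.

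**Working it through.** **Inputs, all from Section 9.2.** Margin 10 ms; assumed effect 4 ms, so the distance to the margin is 10 − 4 = 6 ms; one-sided α = 0.05; SD of ΔQTc 8.5 ms under active drug and under placebo. The section describes 8.5 ms as a within-participant SD, so the SD of the paired difference is 8.5 × √2 = 12.02 ms. Table 2 reproduces only with this √2 factor.

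**1. Reproducing the plan's figure.** Normal approximation:

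n = [(z₀.₉₅ + z₀.₉₀) × SD_diff / 6]² = [(1.645 + 1.282) × 12.02 / 6]² = 34.37.

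Rounded to the nearest integer this is 34, the tabled value; rounded up it is 35. Power at 34 by the same approximation is Φ(6 × √34 / 12.02 − 1.645) = Φ(2.910 − 1.645) = 89.7%.

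**2. The named test.** For a paired t-test with n − 1 degrees of freedom, the noncentrality is (6/12.02) × √n = 0.499 × √n. Power from the noncentral t distribution:

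| n | Power |
|---|---|
| 33 | 87.7% |
| 34 | 88.6% |
| 35 | 89.4% |
| 36 | 90.2% |

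The smallest n for 90% is 36, and for 95% it is 45. Giving the test more error degrees of freedom (2n − 2, or a crossover error term) raises power at 34 only to 89.2–89.3%. At n = 34 the paired t-test reaches 90% only if the SD is at most 8.28 ms or the true effect at most 3.84 ms.

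**3. All of Table 2.** Each cell shows the value for 90% power, then the value for 95%.

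| Effect, SD (ms) | Tabled n | Normal n, unrounded | Paired t, rounded up | Paired-t power at tabled n |
|---|---|---|---|---|
| 3, 8 | 22, 28 | 22.37, 28.27 | 24, 30 | 87.7%, 93.9% |
| 3, 8.5 | 25, 32 | 25.25, 31.91 | 27, 34 | 88.2%, 94.3% |
| 3, 9.5 | 32, 40 | 31.55, 39.87 | 33, 42 | 89.2%, 94.4% |
| 4, 8 | 30, 38 | 30.45, 38.48 | 32, 40 | 88.3%, 94.1% |
| 4, 8.5 | 34, 43 | 34.37, 43.44 | 36, 45 | 88.6%, 94.2% |
| 4, 9.5 | 43, 54 | 42.94, 54.26 | 45, 56 | 89.2%, 94.5% |
| 5, 8 | 44, 55 | 43.85, 55.41 | 46, 57 | 89.3%, 94.4% |
| 5, 8.5 | 49, 63 | 49.50, 62.55 | 51, 64 | 89.0%, 94.7% |
| 5, 9.5 | 62, 78 | 61.83, 78.14 | 64, 80 | 89.5%, 94.7% |

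All 18 tabled values equal the normal n rounded to nearest (49.50 is 49.499 before display rounding). Under the paired t-test all 18 miss their label. Under the normal approximation the 11 that were rounded down miss it, and the 7 that were rounded up meet it.

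**4. Enrolment.** 34 / (1 − 0.20) = 42.5, so 43 would be needed for an expected 34. From 42, the expected number is 42 × 0.80 = 33.6. Keeping 34 of 42 means 81% retained, or 19% dropout.

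**The case against.** The strongest reply is that the figures are right to within ordinary rounding. The text says the power is estimated approximately and always writes approximately 42. The later mention of plain 90% power agrees with 89.7%. Table 2's own range of SDs moves the required n at a 4-ms effect from 30 to 43, which dwarfs a gap of two, and with an SD of 8 ms the paired t-test gives 91.7% at 34. All of this stands as an argument about size. It does not rescue the wording: approximately can cover 89.7% reported as about 90%, but not a claim of more than 90%.

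A reader might infer that the trial is underpowered with no slack. The documents do not support that. The primary analysis is a mixed-effects concentration-QTc model, and Section 9.2 says its gain in precision is left out of the calculation. The PK/QTc population in Section 9.3 also keeps anyone with at least one post-dose concentration-QTcF pair, plus placebo recipients, so 33 completers would not mean an analysis of only 33. The size of these gains is not given, so they cannot establish power above 90% either.

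A reader might also take Table 2 to be wrong on any reading. It is not: 7 of 18 entries meet their label under the formula that reproduces them.

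Finally, if dropouts are assumed independent at 20%, the chance of 34 or more evaluable from 42 is 53%, which might look alarming. But the conventional 43 gives only 65%, because dividing by the retention rate targets the expected number. The figure bears on the word ensure, not on the choice of 42.

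**Conclusion.** The point holds as a small misstatement. On the stated inputs and the named test, power at 34 is 88.6%, which is 1.4 percentage points below 90%; 36 evaluable participants are needed, not 34. No calculation tried that uses 8.5 ms per treatment exceeds 90% at 34. Enrolling 42 falls one short of the 43 needed for an expected 34 at 20% dropout.

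This rests on reading 8.5 ms as the SD under each treatment. Reading it as the SD of the paired difference would give 99.1% at 34, but the text assigns it to both active drug and placebo, and Table 2 does not reproduce without the √2 factor. The sample size itself is not materially wrong, and nothing here calls for more participants.

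**What to change.** Leave enrolment unchanged and correct the text:

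- In Section 9.2, replace the claim of more than 90% power with about 89% power (paired t-test, effect 4 ms, SD 8.5 ms), and bring the later mention of 90% into line.
- Either recompute Table 2 by the paired t-test rounded up, so that the 4 ms / 8.5 ms row reads 36 and 45, or label it as a normal approximation and round up, so that the row reads 35 and 44.
- State the dropout allowance as about 19% (34 of 42 retained), or replace the wording about ensuring at least 34 with expected to give about 34. Make the matching change in the Synopsis and Section 4.1.

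The cost is a few sentences and one table. The stated power becomes slightly less favourable; no participants, visits or analyses are added.
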